It is unknown if in-hospital video education (with repeat viewing post-discharge as desired) that uses symbolic modeling and is aimed at enhancing recognition of and HF self-care response actions to new or worsening dyspnea, fatigue and edema danger signs, (a) *reduces all-cause and HF-related healthcare resource utilization (HCRU)*, (b) *improves perceptions of dyspnea and fatigue*, and (c) *improves self-efficacy for managing symptoms*. Learning the HCRU effects of

NCT-03657459

symbolic modeling video education that explains the most common HF danger signs (dyspnea, fatigue and edema) and provides practical actions to reduce danger signs is important, as the intervention is easy to deploy, uses standard HF self-care behavior expectations, and is practical to use in hospital and home environments.

It is important to learn the *time to the video intervention effect* on (a) HCRU outcomes and (b) perceptions of fatigue, dyspnea and self-efficacy for managing HF symptoms. The intervention may have an early effect (30-days) that wanes over time, have a steady effect over a 6-month period, or the effect may be slow to peak (i.e., 90 or 180 days) as patients may learn through a recognition and self-care action “trial and error” approach.

Finally, the video intervention effect on outcomes may differ based on *after hospital discharge viewing by patients and/or family supporters*, as repeated viewing and/or family supporter viewing of danger signs and HF self-care actions may facilitate *earlier recognition* of warning signs and/or *earlier or more accurate adherence* to HF self-care actions that lead to improved HCRU outcomes, lower perceptions of fatigue and dyspnea and improved self-efficacy for managing symptoms.

Study Purposes

The purposes of this study are to examine the effects of HF danger signs videos (1 each on dyspnea, fatigue and edema) that include 2 key features: (1) recognition of each danger sign and (2) common, simple, practical self-care actions known to reduce HF danger signs ([a] fatigue: recognizing that it may be due to dehydration and adhering to physical activity and exercise expectations; [b] dyspnea and edema: adhering to a low sodium diet and fluid intake limitations; [c] all 3: contacting a doctor when appropriate). Based on Bandura’s social cognitive theory symbolic modeling, video content is meant to increase self-efficacy for independently completing self-care actions when dyspnea, fatigue and/or edema are present.

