The following outcomes will be assessed:

PRIMARY

1. 30 ± 6 days *first occurrence* of post-discharge **HF-related** HCRU; defined as hospitalization, emergency department [ED] visits, death or cardiac transplantation/ ventricular assist device [VAD] implant-- individual components and combined),

SECONDARY:

2. 90- and 180-day ± 6 days *first occurrence* of post-discharge **HF-related** HCRU; defined as hospitalization, emergency department [ED] visits, death or cardiac transplantation/ ventricular assist device [VAD] implant-- individual components and combined),
3. 30-, 90- and 180-day ± 6 days *first occurrence* of post-discharge **all-cause** HCRU; defined as hospitalization, emergency department [ED] visits, death or cardiac transplantation/ ventricular assist device [VAD] implant-- individual components and combined),
4. 30-, 90- and 180-day ± 6 days *time to* first occurrence of **all-cause** and **HF-related** post-discharge HCRU (individual components and combined),
5. 30-, 90- and 180-day ± 6 days *total all-cause* post-discharge HCRU (individual components and combined);
6. 30-, 90- and 180-day ± 6 days *total HF-related* post-discharge HCRU (individual components and combined);

NCT-03657459

7. Change in *functional status* from baseline to 30-, 90- and 180-days \pm 6 days after hospital discharge,
8. Change in *dyspnea scores* from baseline to 30-, 90- and 180-days \pm 6 days after hospital discharge,
9. Change in *fatigue scores* from baseline to 30-, 90- and 180-days \pm 6 days after hospital discharge, and
10. Change in *self-efficacy for managing symptoms* from baseline to 30-, 90- and 180-days \pm 6 days after hospital discharge
11. Differences in primary and secondary outcomes (1-10) among *intervention-group participants*, after creating 3 sub-groups based on post-discharge video viewing ([a] total number of times videos were watched, [b] viewed by caregivers/family in the hospital, and [c] viewed by caregivers/family post hospital discharge.

Specific aims and hypotheses:

1. Determine the effects (and time to effects) of HF danger signs education on *first occurrence*, *time to first occurrence* and *total* all-cause and HF-related HCRU after hospital discharge: hospitalization, ED visit, death, cardiac transplantation or VAD.
2. Examine if functional status, dyspnea, fatigue and self-efficacy for managing symptoms scores change over time and the direction of change.

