3. Among intervention group participants, determine if post-discharge re-viewing of danger signs education by patients and/or viewing content by family supporters is associated with differences in HCRU, functional status, dyspnea, fatigue and self-efficacy for managing symptoms, including time to effects.

Hypothesis 1a: 30-day post-discharge HCRU will be lower or trend toward lower, and 90-, and 180-day *first occurrence*, and *total* HCRU will be lower in the HF video danger education group compared to the usual care group.

Hypothesis 1b: *Time to first* HCRU occurrence will be longer at 30-, 90- and 180-days in the HF video danger education group compared to the usual care group.

Hypothesis 1c: *Total* HCRU will be lower at 30-, 90- and 180-days in the HF video danger education group compared to the usual care group.

Hypothesis 2a: *Functional status* scores improve at 30-days and remain lower over time in the HF video danger education group compared to the usual care group.

Hypothesis 2b: *Dyspnea* scores improve at 30-days and remain lower over time in the HF video danger education group compared to the usual care group.

Hypothesis 2c: *Fatigue* scores improve at 30-days and remain lower over time in the HF video danger education group compared to the usual care group.

Hypothesis 2d: *Self-efficacy for managing symptoms* scores are higher at 30-days and remain higher over time in the HF video danger education group compared to the usual care group.

NCT-03657459

Hypothesis 3a: Repeat viewing of videos by patients, compared to 1-time viewing in-hospital and/or viewing of videos by family supporters/caregivers in hospital and/or post discharge, compared to viewing only by patients will be associated with *longer time to first HCRU and lower total HCRU*.

Hypothesis 3b: Repeat viewing of videos by patients, compared to 1-time viewing in-hospital and/or viewing of videos by family supporters/caregivers in hospital and/or post discharge, compared to viewing only by patients will be associated with *improved functional status* and *dyspnea and fatigue scores* (due to heightened awareness of danger signs, heightened recognition of worsening of danger signs)

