After completing baseline paperwork, patients will be randomly assigned to the usual care or usual care plus HF danger signs video education group using block randomization; with blocks of 20, to decrease the influence of external factors that could alter outcomes. The randomization assignment will be made by a QHS statistician.

After randomization to groups:

- Intervention group patients will receive usual hospital care and also, HF danger signs education via iPad by research personnel. Danger signs education can be administered at the time of enrollment. There is no need to wait until day of discharge, since HF danger sign messages are not individualized and discharge is a very busy time. Immediately prior to discharge, patients' focus may be on preparing to leave the hospital and not on education about HF, especially if patients believe that they have accurate perceptions of HF danger signals, even though in previous research, most subjects did not.
- Usual care group patients will be educated by their healthcare providers (including nurse/other caregivers). Education may include Elsevier HF videos that are shown on Cleveland Clinic hospital televisions.

A research nurse will use telephone calls or mailing methodologies to have the following 4/5 tools (40/43 items in total for usual care and intervention groups, respectively) completed at 30 ± 6 days: functional status, dyspnea, fatigue, self-efficacy for managing symptom and video watching experiences. Administration of functional status, dyspnea, and fatigue questionnaires will be randomly ordered (counterbalanced). The intervention-only group survey on video watching experiences will be administered last. It is expected that data collection will take ~ 10 minutes or less.

A research nurse will review EMRs of enrolled patients after the index (baseline) hospital discharge and at 30-, 60-, 90- and 180-days (± 6 days) for HCRU events.

- If not found in the EMR, telephone calls will be made to gather data.
- At baseline, research nurses will obtain home telephone number and the telephone number of a close relative or friend that can provide patient contact information, as needed.

NCT-03657459

Analyses

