Patient characteristics will be summarized overall and by randomized group using frequencies and percentages for categorical factors and means and standard deviations for continuous measures. First occurrence HCRU use (**all-cause and HF-related**) will be compared using Pearson chi-square tests. Time to first HFCU use will be summarized using Kaplan-Meier estimates, and compared using log-rank tests and Cox proportional hazards models. Total HCRU use will be compared using Poisson regression models. Linear mixed effect models will be used to evaluate trends in functional, dyspnea, fatigue, and self-efficacy measures over time and, if trends significantly differ, comparisons within time point will be performed. Secondary analyses will use similar methods to compare patients in the video group, stratified by video viewership, on the same outcomes. If appropriate, exploratory analyses will also be performed, comparing the above outcomes between treatment groups, adjusting for any patient characteristics that differ between randomized groups. Analyses will be performed using SAS software (version 9.4; Cary, NC), and an overall significance level of 0.05 will be assumed for all endpoints. Comparisons between the 3 subgroups of patients in the video group will use Bonferroni corrected significance criteria to preserve the overall error rate when making multiple comparisons.

Feasibility

The main campus of Cleveland Clinic has a high volume of HF discharges each year. Other hospitals in the system have moderate volumes of HF discharges, and are less likely to have patients who meet exclusion criteria due to enrollment in another research study or non-ambulatory NYHA FC IV (advanced) HF. Electronic medical records allow for review of data on events that occur in *all* system hospitals and regional medical practice ambulatory care sites; decreasing the need to rely on patient recall of HCRU.

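### The 30-day comparison of the patient-reported scales depends on a trend test and names no baseline adjustment, which costs power for Hypotheses 2a to 2d

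*Combined protocol and SAP*

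**What the plan says.** - **Analysis (Analyses section).** "Linear mixed effect models will be used to evaluate trends in functional, dyspnea, fatigue, and self-efficacy measures over time", and then: "if trends significantly differ, comparisons within time point will be performed". The section does not say whether time is linear or categorical, whether baseline is a response or a covariate, or which contrast tests the trends. The only covariate adjustment is exploratory and covers patient characteristics found to differ between the arms. The baseline score is not named.
- **Hypotheses (Specific aims and hypotheses).** Hypotheses 2a to 2c each state that "scores improve at 30-days and remain lower over time in the HF video danger education group compared to the usual care group". Hypothesis 2d has the same form, with higher self-efficacy scores.
- **Outcomes 7 to 10 (Study Purposes).** Each is a change in score "from baseline to 30-, 90- and 180-days".
- **Schedule (Data Collection).** The scales are completed at baseline, before randomization. After discharge the tools are to be "completed at 30 ± 6 days: functional status, dyspnea, fatigue, self-efficacy for managing symptom and video watching experiences". No later administration is scheduled. The Feasibility section limits the later telephone calls to HCRU data missing from the records.
- **Other effect shapes (Introduction).** "The intervention may have an early effect (30-days) that wanes over time". A steady effect and a slow-to-peak effect are also allowed for.

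**The concern.** A hypothesis that names a time point should be answered by an estimate at that time point. Here the estimate is promised only after a different test has reached significance. If that test fails, the plan promises no between-arm result at 30 days for that scale, not even an interval.

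The test that decides this may also be weaker than it need be. The trial measures each scale before randomization, and using that score as a covariate is the standard way to gain precision at no cost. The plan does not commit to it. At stake are four secondary outcomes and the whole of Hypothesis 2.

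**Working it through.** **1. The plan's own figures.** The only sizing is for first HF-related HCRU. A two-sided chi-square test of 28% against 28% × 0.67 = 18.76% with 329 per arm gives 80.1% power. For 46% against 34.5% at 90 days, power is 85.4%. Both reproduce the stated 80% and 85%. Nothing is given for the scales: no effect size, SD or correlation.

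**2. Assumptions.** Unit SD, equal correlation ρ between any two visits (0.3, 0.5 or 0.7), complete data, two-sided 0.05, n per arm, and day-30 effect d in SD units. Write k = d√(n/2).

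**3. The tests as scheduled (baseline and day 30).** With two time points, linear and categorical time are the same model. Unless baseline means are constrained equal, the arm-by-time term is the difference in mean change.
- Baseline-adjusted day-30 contrast: signal k/√(1−ρ²)
- Change comparison: signal k/√(2(1−ρ))
- Variance ratio, adjusted to change: (1−ρ²)/(2(1−ρ)) = (1+ρ)/2 = 0.65, 0.75, 0.85. Adjustment therefore lowers variance by 35%, 25%, 15%.

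**4. Scale the effect so that the adjusted contrast has 80% power.** Its signal is then 2.80, so k = 2.80√(1−ρ²).

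| ρ | k | Change signal | Change-test power |
|---|---|---|---|
| 0.3 | 2.67 | 2.67/√1.4 = 2.26 | 62% |
| 0.5 | 2.43 | 2.43/√1.0 = 2.43 | 68% |
| 0.7 | 2.00 | 2.00/√0.6 = 2.58 | 73% |

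With 329 per arm, d = k√(2/329), or about 0.21, 0.19 and 0.16 SD.

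**5. If days 90 and 180 were also collected.** Take a step effect (0, 1, 1, 1) × d at days 0, 30, 90, 180. The mean day is 75 and the deviations are −75, −45, 15, 105. Their squares sum to 18,900, and their product with the step is −45 + 15 + 105 = 75.
- Linear time: signal 75k/√(18,900(1−ρ)) = 1.74, 1.87, 1.99. Power is **41%, 46%, 51%**.
- Categorical time including baseline, 3-df interaction: noncentrality 0.75k²/(1−ρ) = 7.65, 8.83, 10.01. Power is **63%, 70%, 76%**.

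**6. Sensitivity to effect size, 329 per arm, baseline and day 30.**

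| d | Test | ρ = 0.3 | ρ = 0.5 | ρ = 0.7 |
|---|---|---|---|---|
| 0.20 | Change | 58% | 73% | 91% |
| 0.20 | Adjusted | 77% | 84% | 95% |
| 0.25 | Change | 77% | 89% | 98% |
| 0.25 | Adjusted | 92% | 96% | 99% |

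The loss is always in the same direction and shrinks as the effect or the correlation grows.

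**The case against.** The strongest reply is that the trend test is a legitimate between-arm test in its own right. With baseline and day 30 only, it tests the day-30 change that outcomes 7 to 10 define. Aim 2 asks whether scores change over time and in which direction, and a longitudinal model suits that aim. This stands, and it limits the point in three ways.

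- **A reader might infer that the condition blocks an early, sustained effect.** The documents do not support this. As scheduled, a 30-day effect is itself a trend difference. The test would be blind to a constant difference, passing only 5% of the time, if baseline were left out of the model. No section says so, and the outcomes are defined from baseline.
- **A reader might infer that real effects would never be tested.** They would be, by the trend test. What may be missing is the day-30 estimate.
- **A reader might infer that the follow-on comparison ignores baseline.** The plan is silent on this. If it were unadjusted, passing both steps would have 55%, 53% or 43% power in the setting of step 4, but that method is not stated. A mixed model with baseline means constrained equal would fit the present wording and avoid the variance penalty.

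Much of the shortfall also comes from the missing adjustment and not from the condition. In the same setting an unconditional, unadjusted day-30 comparison has about 76%, 68% or 52% power, so at ρ = 0.5 it equals the change test and at 0.7 it is weaker.

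Finally, a preliminary test can limit multiplicity. As scheduled there is one follow-up time per scale, so it limits little. It does not control error across the four scales in any case: four independent tests at 0.05 give 1 − 0.95⁴ = 18.5%.

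**Conclusion.** The concern holds as a loss of power and an incomplete specification. The 30-day comparison is conditional on a significant trend difference although Hypotheses 2a to 2d name 30 days, and no baseline adjustment is committed to.

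With the scheduled data, and unless baseline is constrained equal, the conditioning test has 62%, 68% or 73% power where a baseline-adjusted contrast has 80%. The larger loss, to 41%, 46% or 51%, needs two things that the plan does not establish: scores at 90 and 180 days, and linear time.

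All these figures rest on assumed correlations and an effect scaled to 80% power. At 0.25 SD with 329 per arm and correlation 0.7, the loss is about one percentage point. The outcomes are secondary, and the primary HCRU result does not depend on this.

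**What to change.** In the Analyses section, for each of the four scales:

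1. Name the between-arm difference at day 30, adjusted for the baseline score, as the estimate of interest. Use ANCOVA, or a mixed model with categorical time and baseline either as a covariate or constrained equal between arms.
2. Report it with a 95% CI whatever the trend test shows.
3. Estimate the same contrast at any later time at which the scale is actually measured. Reconcile the 90- and 180-day score outcomes with the data collection schedule, because persistence cannot be assessed from day 30 alone.
4. Label these contrasts as secondary results, since the trend test will no longer limit the number of time-point comparisons.

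Items 1, 2 and 4 cost SAP wording only, with the same patients, data and software. The looser control over time-point comparisons is a small downside. Under item 3, adding later administrations would cost more; aligning the text with the schedule would not.

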The fatigue and dyspnea video's will be viewed back-to-back and the edema video will be added for patients with a history of edema. There are 4 versions of each video: (1) based on race (Caucasian and African-American) and sex (male and female)—to promote symbolic modeling— by patients who look like video models (as stated in the introduction). Scripts for each video were developed jointly by [name], Director of Media and Education for Wellflix, Inc. and [name] PhD, principal investigator and clinical nurse specialist in HF. Content includes recognition and assessment of fatigue, dyspnea and edema and specific actions to take to reduce the danger signs or prevent worsening (dietary sodium and/or fluid restriction, physical activity/exercise and contacting the doctor).

Overall video viewing time for all 3 videos is 9:50 minutes; the fatigue and dyspnea videos that all intervention patients will view are 6:50 minutes:

- *Fatigue* is 2:20 minutes + end text list= 3:00 minutes;

NCT-03657459

- *Dyspnea* is 1:40 minutes + dyspnea “yes” or “no” management (2 options; patient selects the option that matches current status) = 3.50 minutes
- *Edema* is 2:40 minutes + end text list= 3:00 minutes;

During hospitalization, videos will be loaded into an iPAD and will be viewed through the iPAD.

Patients have an opportunity to view videos post-discharge as desired and able. *Post discharge*, videos can be in 2 ways: (1) via the Wellflix, Inc. site at www.wellflix.net/DangerSignsCC or (2) by DVD player (DVD created by Wellflix, Inc for this research), for patients who have DVD player capability and prefer this method.

NOTE, at/after 180-day follow up data are collected, *usual care group* patients will be offered access to Wellflix, Inc. videos used in this research study via mailing of a handout sheet developed specifically for them (that contains the web address and a note of encouragement to view the videos.

Outcomes and Measurement

HCRU. Includes all-cause and HF-related hospitalization, ED visit, death, cardiac transplantation, or VAD placement at 30-, 90-, and 180-days \pm 6 days in both groups. Data will be retrieved from medical records when available or via telephone call to patients.

- Patients will receive a calendar to keep track of HCRU events in-between phone calls.
- Research nurses will use a case report form to record HCRU events

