Patient characteristics and medical history at baseline. Standard patient characteristics that are used in many research studies of patients with HF, will be used in this research as they span themes of interest and provide global information about participants. Items include height and weight, highest education, comfort living on current household income, current signs and symptoms of HF, comorbid conditions and billing data retrieved from Cleveland Clinic billing database (age, race, gender, marital status, discharge disposition, and length of hospital stay). The *Charlson Comorbidity Index* will be used to collect medical comorbidity history. This index was developed to classify comorbid conditions which might change the risk of mortality.²⁴⁻²⁹ The score will be categorized into 3 groups (score of 1-2 = 1; 3-4 = 3; 5 or more = 5). In one study with 33,940 patients with ischemic heart disease, the grouping demonstrated a strong relationship with mortality rate.²⁹ In 2011, the tool was reduced from 19 items to 12 items and each item was re-scored based on morbidity and mortality of medical conditions in the current era of medical therapies.³⁰ This data will also be used to describe the sample groups for similarity in acuity.

Video Watching Experiences in-hospital and at 30 day follow-up (intervention group only). A 3-item, investigator-developed survey will assess video watching characteristics: total number of watching’s, caregiver/family member video watching *in the hospital*, and

NCT-03657459

caregiver/family member video watching *in the post discharge* period, up to 30 days. Items use choose-the-best-response options.

Data Collection

Medical records will be assessed for inclusion and exclusion criteria before approaching patients. Research personnel will explain the study in a patient's room (in non-private rooms, a curtain will be drawn to separate beds and enhance confidentiality). After received verbal informed consent, patients will complete baseline data that includes assessment of functional status, dyspnea, fatigue and self-efficacy for managing symptoms immediately before hospitalization. Administration of the functional status, dyspnea and fatigue questionnaires will be randomly changed for each participant to allow for counterbalancing, since there item themes may have overlap/be similar. Baseline data collection should take 10 minutes or less.

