- At 30-day follow-up, there are 2 options to collect data on 4 tools with 40 items in total, that will take ~ 10 minutes or less to complete (usual care group) or 5 tools with 43 items in total, that will take ~ 10 minutes to complete (intervention group) and include functional status, dyspnea, fatigue self-efficacy, and a 3-item video viewing experience survey for the intervention group, by telephone or mail. As a secondary method, patients who are hospitalized during the follow-up period may receive tools in person by a research nurse.

Limitations and Anticipated Problems

Patients and caregivers may never view the Wellflix, Inc. HF danger sign videos after discharge, and/or forget content viewed during hospitalization. Patients may view/hear, but ignore, message content. Patients may drop out before the 180-day follow-up data collection. Analyses will be completed using “intent to treat” methods. In this way, we will be able to learn the effect size of the intervention among all patients randomized to the intervention group.

No adverse effects are anticipated, as the intervention in this research are HF danger signs videos that cannot create harm to patients. Video scripts provide messages that may be available in commercially available videos and or written materials used in usual HF care education and discharge instruction materials. There are no risks of adverse events from the intervention itself.

Human Subjects Protection

Approval by the Cleveland Clinic Institutional Review Board will be sought prior to study initiation. We believe this study is minimal risk as the intervention is composed of back-to-back video viewing of 3 HF danger signs (fatigue, dyspnea and edema). Video self-care messages delivered through demonstration, imitation and modeling are part of usual heart failure post-discharge care, but are delivered using principles of Bandura’s social learning theory, to enhance ability to complete independently after viewing videos.

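### In the video arm, home viewing and HCRU build up over the same 30 days, so comparing HCRU by viewing can show an association when viewing has no effect

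*Combined protocol and SAP*

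**What the plan says.** Aim 3 (Specific aims and hypotheses) is to "determine if post-discharge re-viewing of danger signs education by patients and/or viewing content by family supporters is associated with differences in HCRU" and in the symptom, function and self-efficacy scores, including time to effects. Hypothesis 3a gives the direction: more viewing should go with a longer time to first HCRU and less total HCRU. Secondary outcome 11 applies the split to outcomes 1–10, which include the 30-day primary endpoint. It names three viewing measures: total viewings, family viewing in hospital, and family viewing after discharge.

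Home viewing is voluntary (Intervention): "Patients have an opportunity to view videos post-discharge as desired and able". The three-item survey in Outcomes and Measurement asks for total viewings, family viewing in hospital, and family "video watching *in the post discharge* period, up to 30 days". No item is described as recording dates. Data Collection has the tools "completed at 30 ± 6 days: functional status, dyspnea, fatigue, self-efficacy for managing symptom and video watching experiences". Feasibility adds that "patients who are hospitalized during the follow-up period may receive tools in person by a research nurse".

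HCRU is counted from index discharge. The Analyses section states: "Secondary analyses will use similar methods to compare patients in the video group, stratified by video viewership, on the same outcomes". For HCRU, those methods are Pearson chi-square tests, Kaplan-Meier estimates with log-rank tests and Cox models, and Poisson regression. A Bonferroni correction covers comparisons between three subgroups.

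**The concern.** Patient repeat viewing and family viewing after discharge are not known at time zero. They accrue while HCRU is already being counted, and the plan treats them as if they were fixed at discharge. An early event can then shape the exposure in three ways:

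- A readmission can interrupt home viewing, or it can prompt more of it.
- A patient who dies before the survey cannot report any viewing.
- A patient in hospital may be surveyed in person, so an event can also change how viewing is recorded.

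If events curtail viewing, viewers look better, which is the pattern Hypothesis 3a predicts. If events or worsening symptoms prompt viewing, viewers look worse and a real association may be hidden. Bonferroni controls multiplicity and does nothing about this. Intention-to-treat protects the randomised comparison, not a split made after discharge.

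The scope is narrow. In-hospital viewing precedes time zero and is free of this problem. The randomised comparisons are untouched, and nothing is claimed about Hypotheses 3b and 3c.

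**Working it through.** **Inputs from the plan** (Sample section): 329 evaluable patients per group; 30-day rate 28%, or 18.8% under the target effect; 90-day rate 46%, or 34.5%. The sample size reproduces. With p₁ = 0.28 and p₂ = 0.28 × 0.67 = 0.1876, n = [1.960√(2 × 0.2338 × 0.7662) + 0.842√(0.2016 + 0.1524)]² / 0.0924² = 328.2, so 329. Then 329/0.9 = 365.6, so 366. Power at 90 days is 85.4%. The sample size is not in dispute.

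**Assumed, not in the documents:** home-viewing uptake, and what happens to viewing after an event.

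**Closed form: constant hazards, no viewing effect, viewing stops at the first event.** Let p = 0.28 and let q = 0.5 be the share who would view by day 30 if event-free.

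- Cumulative hazards over 30 days: event −ln 0.72 = 0.3285; viewing −ln 0.5 = 0.6931.
- P(event before any viewing) = 0.3285/1.0216 × (1 − 0.72 × 0.5) = 0.206.
- P(viewed, then event) = 0.280 − 0.206 = 0.074.
- HCRU in viewers = 0.074/(0.074 + 0.360) = 17.1%.
- HCRU in non-viewers = 0.206/(0.206 + 0.360) = 36.4%.
- Risk ratio = 0.47, although viewing does nothing.

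**Simulation of the same model** (2,000 null trials per setting, 28% rate, two-sided 0.05; 20%, 50% and 80% viewers):

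| Viewing after first event | 30-day risk ratio | Chi-square rejects |
|---|---|---|
| unchanged | 0.99, 1.00, 0.99 | 5%, 5%, 5% |
| pauses 7 days | 0.83, 0.79, 0.73 | 11%, 26%, 37% |
| stops | 0.53, 0.47, 0.38 | 63%, 98%, 100% |
| doubles | 1.39, 1.56, 1.95 | 40%, 69%, 66% |

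When viewing stops, rejection at 0.05/3 is still 42%, 94% and 100%. At the 18.8% rate, stopping gives risk ratios of 0.50, 0.44 and 0.33, with 47%, 92% and 99.7% rejection at 0.05.

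**Wider simulation** (240 settings, 2,000 null trials each). Weibull hazards were fitted to the plan's 30- and 90-day rates and extrapolated to day 180. Also assumed: uptake 10–86%, survey day uniform on 24–36, 10% fatality, non-HF 30-day risk 10–20%, shared frailty variance 0 or 1. Patients dead before the survey were excluded. False positives at 0.05 for HF-related HCRU:

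| Effect of an event on viewing | 30-day chi-square | Log-rank, discharge to day 180 |
|---|---|---|
| 1 day lost | 4–6% | 4–7% |
| 5 days lost | 4–20% | 4–15% |
| 10 days lost | 5–63% | 5–46% |
| stops | 17–100% | 7–100% (HR 0.31–0.82) |
| rate doubled | 19–76% | 13–49% (HR 1.19–1.41) |

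At 0.05/3 (nominal 1.7%), five days lost gives 1–11% for the chi-square test.

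**Does a day-30 landmark remove it?**

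- *First event.* Requiring freedom from HF events only leaves up to 21% false positives. Requiring freedom from any HCRU event gives 4–6% in all 240 settings (HR 0.97–1.04). The simpler model gives 4.2–6.2%.
- *Death alone* (48 settings, viewing stops, early events raising later mortality 2–3-fold). Requiring only survival to day 30 gives 3–48%; requiring freedom from any event gives 3–6%.
- *Total HF-related HCRU to day 90* (120 settings, 1,000 trials each, Poisson with robust standard errors). Counting from discharge gives 4–100%. Counting after day 30 only gives up to 67%; adding the early HF count, up to 15%; adding the early all-cause count, 3.5–7.9%.
- *Self-selection remains.* If the higher-risk half watches at half the rate, the landmark analysis still rejects in 9–46% of null trials (HR 0.61–0.82).

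**The case against.** The strongest objection is that everything turns on viewing after an event, which the documents do not describe. If an event costs a day of viewing, error rates are nominal. The extreme figures need viewing to stop for good, even after an ED visit, although web and DVD access continue. This stands: the figures show sensitivity and are not an estimate. But the survey as described has no dates from which the question could be settled later.

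Second, the analysis is secondary and worded as an association, and self-selection would remain in any case. That is true and limits the weight of the point. Still, this is one of three aims, with a directional hypothesis and corrected tests, and event timing can create the association itself.

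Third, the landmark has its own costs. It discards the first 30 days, which Aim 3 wants examined. It also conditions on events that viewing might prevent: with frailty variance 1, a true rate ratio of 0.70 is estimated as about 0.76–0.77, though without frailty there was no material attenuation. This bias is towards no effect and creates no false positives, but the SAP should state it. The total-HCRU, death-only and self-selection figures each come from a single model, and the plan does not specify the robust standard errors used for total HCRU. The count-adjusted Poisson analysis is only close to nominal.

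**Conclusion.** The concern holds and should be fixed. For patient repeat viewing and family viewing after discharge, the planned HCRU comparisons let the outcome influence the exposure, and nothing in the Analyses section prevents it. The mechanism follows directly from the documents. Its size does not: false-positive rates run from nominal to 100%, in either direction, depending on assumed uptake and viewing after an event. The 90- and 180-day outcomes counted from discharge carry the same 30-day overlap in diluted form.

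**What to change.** For patient repeat viewing after discharge and family viewing after discharge only:

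1. Analyse first and time-to-first HCRU from day 30, among video-arm patients alive and free of any HCRU event by then. Use all-cause freedom even when the outcome is HF-related or a single component. Count later events to days 90 and 180.
2. For total HCRU, count events after day 30 among patients alive at day 30, with the number of earlier all-cause events (0, 1, 2 or more) in the Poisson model.
3. Report 30-day HCRU by these exposures as descriptive only.
4. Ask about viewings from discharge to day 30 separately from viewings in hospital. Classify patients surveyed before day 30 by what they report then. For those surveyed later, do not count viewing after day 30.

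Keep discharge as time zero for in-hospital viewing. State that the landmark removes the timing bias but not self-selection, that it may attenuate a true effect, and that results are associational. Adjust for the baseline characteristics already collected. Separately, secondary outcome 11 lists three overlapping viewing variables while Analyses compares three subgroups. Reconcile the two and say which comparisons the Bonferroni correction covers.

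The cost is SAP wording and one survey item. Aim 3's time to effects is then answered only after day 30. From 329 patients, 189–219 remain with 75–94 HF-related events to day 180 at the 28%/46% rates, or 213–245 with 66–87 at 18.8%/34.5%. This assumes 10–20% non-HF 30-day risk and makes no allowance for survey non-response among survivors. By Schoenfeld's formula, ln HR = −(2.394 + 0.842)/√(D·π(1−π)), where D is the number of events and π the share of viewers. With 20–60% viewers, 80% power at 0.05/3 needs an HR of about 0.37–0.51 or lower. For all-cause HCRU (101–130 events) it needs 0.45–0.57. If that is judged too little, labelling all HCRU results by these two exposures descriptive is the simpler course.
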